3.1.2.3 Imaging

As in the dose escalation phase, all imaging will be sent to the central imaging core laboratory for independent review as soon as possible within 48 hours of acquisition. Further instructions will be provided by the imaging core laboratory in separate guidelines.

Patients in the dose expansion phase will undergo planar WB scans, SPECT/CT scans, diagnostic CT scans, and brain MRIs, as shown in [Table 2](#). As in the dose escalation phase, imaging to evaluate the organ/target lesion uptake will be performed after each CAM-H2 administration; however, it will be performed less frequently. Imaging to evaluate disease progression will be performed as done in the dose escalation phase (see [Section 3.1.1.3](#)).

Table 2. Imaging During the Dose Expansion Phase

Type of Imaging	Cycle 1	Cycle 2
Planar WB scans for PD distribution and evaluation of organ/target lesion uptake	After each dose (Dose 1 and Dose 2): • 24 hours (\pm 4 hours) after CAM-H2 [1].	After each dose (Dose 1 and Dose 2): • 24 hours (\pm 4 hours) after CAM-H2 [1].
SPECT/CT scans to evaluate organ/target lesion uptake	After each dose (Dose 1 and Dose 2): • 24 hours (\pm 4 hours) after CAM-H2.	NA
Diagnostic CT scans to evaluate disease status	At screening and after Dose 2 only [2]: • 4 weeks after CAM-H2 at Visit 10 (Week 8); and • Every 8 weeks after Visit 10 (Week 8), as long as the patient had clinical benefit after Cycle 1 [3] and there is no disease progression.	After Dose 2 only [2]: • 4 weeks after CAM-H2 at Visit 19 (Week 8); • At Visit 20 (Week 11/EOT); and • Every 8 weeks after Visit 20 (Week 11), as long as there is no disease progression.
Brain MRI scans to evaluate disease status [4]	At screening and after Dose 2 only [2]: • 4 weeks after CAM-H2 at Visit 10 (Week 8); and • Every 8 weeks after Visit 10 (Week 8), as long as the patient had clinical benefit after Cycle 1 [3] and there is no disease progression.	After Dose 2 only [2]: • 4 weeks after CAM-H2 at Visit 19 (Week 8); • At Visit 20 (Week 11/EOT); and • Every 8 weeks after Visit 20 (Week 1), as long as there is no disease progression.

1. During Dose 1 of the cycle, the first planar WB scan will also serve as the PD distribution scan.
 2. Imaging to evaluate disease status after treatment will start 4 weeks after the last CAM-H2 infusion (Dose 2) of the cycle at Week 8. If a patient cannot receive Dose 2 of a given cycle, his/her imaging to evaluate disease status will start at the theoretical timing for Dose 2 (ie, 4 weeks after Dose 1 of the cycle).
 3. Patients without clinical benefit after Cycle 1 will have another diagnostic CT scan and brain MRI (if indicated) at Visit 11 (Week 11), which will be EOT.
 4. Brain MRI will only be performed in patients with known brain metastases.

CT = computed tomography; EOT = End of Treatment; MRI = magnetic resonance imaging; NA = not applicable; PD = pharmacodynamic(s); SPECT = single photon emission computed tomography; WB = whole body.

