Diagnostic CT scans to evaluate disease status	
At screening and after Dose 2 only [3]:
 
 • 4 weeks after CAM-H2 at Visit 10 (Week 8); and • Every 8 weeks after Visit 10 (Week 8), as long as the patient had clinical benefit after Cycle 1 [4] and there is no disease progression. 	
After Dose 2 only [3]:
 
 • 4 weeks after CAM-H2 at Week 8; and • Every 8 weeks after Week 8, as long as the patient had clinical benefit after the current cycle [4] and there is no disease progression.
Brain MRI scans to evaluate disease status [5]	
At screening and after Dose 2 only [3]:
 
 • 4 weeks after CAM-H2 at Visit 10 (Week 8); and • Every 8 weeks after Visit 10 (Week 8), as long as the patient had clinical benefit after Cycle 1 [4] and there is no disease progression. 	
After Dose 2 only [3]:
 
 • 4 weeks after CAM-H2 at Week 8; and • Every 8 weeks after Week 8, as long as the patient had clinical benefit after the current cycle [4] and there is no disease progression.

 1. Patients with a negative PD distribution scan will not be treated further, although they will be included in the SAF. An extra patient will then be included in the same cohort as substitute. 2. During Dose 1 of the cycle, the first planar WB scan will also serve as the PD distribution scan. 3. Imaging to evaluate disease status after treatment will start 4 weeks after the last CAM-H2 infusion (Dose 2) of the cycle at Week 8. If a patient cannot receive Dose 2 of a given cycle, his/her imaging to evaluate disease status will start at the theoretical timing for Dose 2 (ie, 4 weeks after Dose 1 of the cycle). 4. Patients without clinical benefit after the current cycle will have another diagnostic CT scan and brain MRI (if indicated) at Week 11, which will be EOT. 5. Brain MRI will only be performed in patients with known brain metastases. 		

CT = computed tomography; EOT = End of Treatment; MRI = magnetic resonance imaging; NA = not applicable; PD = pharmacodynamic(s); SAF = Safety Analysis Set; SPECT = single photon emission computed tomography; WB = whole body.
		

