3.1.3 Long-Term Follow-Up Period

A long-term follow-up period will start after the EOT/Early Termination (ET) Visit. Follow-up will continue for a maximum of 12 months. All patients without disease progression will be monitored every 8 weeks to evaluate PFS for a maximum of 12 months or until disease progression, death, or consent is withdrawn, whichever occurs first.

The bi-monthly visits will consist of imaging to evaluate disease status, performance status evaluation using the Eastern Cooperative Oncology Group performance status (ECOG PS), and assessment for any post-investigational treatment. Other changes in medical history or concomitant medications and AEs will be assessed. Imaging to evaluate disease status will begin 8 weeks after the last diagnostic CT scan or brain MRI performed during the study treatment period. Diagnostic CT scan will be performed in all patients. Brain MRI will only be performed in patients with known brain metastases. Patients with extracranial lesions will be evaluated for progression using RECIST version 1.1. Patients with brain metastases without extracranial lesions will be evaluated for progression using RANO-BM. Patients with extracranial lesions and brain metastases will be evaluated for progression using both RECIST version 1.1 (extracranial lesions) and RANO-BM (brain metastases). Additional details are provided in the Imaging Review Charter.

As long as there is no disease progression, imaging to evaluate disease status will be performed every 8 weeks.

For patients with disease progression or starting alternative anticancer therapy, imaging to evaluate disease status will be performed according to the local site standard of care. Review of images at this point will be done locally and not by the central imaging core laboratory. Additionally, those patients will no longer be followed every 8 weeks, but every 12 weeks, to assess survival, disease status, and post-progression therapy. Follow-up contacts (by clinic visits or telephone call) will be performed every 12 weeks until death, lost to follow-up, study end (12 months post-last patient EOT/ET Visit), or study termination by the Sponsor, whichever occurs first.

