6.2.2.8 Visit 10 (Week 8)

The following procedures will be performed at Visit 10 (Week 8):

- Assess AEs;
- Perform physical examination;
- Measure vital signs;
- Perform clinical laboratory tests;

Note: Clinical laboratory tests should be performed prior to any imaging.

- Perform urinalysis for kidney biomarkers and for microscopic evaluation of sediment;

- Assess performance status using the ECOG PS; and
- Perform imaging to evaluate disease status.

Note: Diagnostic CT scan will be performed in all patients. Brain MRI will only be performed in patients with known brain metastases.

6.2.2.9 Visit 11 (Week 11): End of Treatment Visit or Cycle 2 eligibility assessment

This visit will also serve as the screening visit for Cycle 2 of the dose escalation phase. Cycle 2 eligibility will be assessed by evaluating disease state and safety. This visit will serve as the EOT Visit for patients who do not have CB.

The following procedures will be performed at Visit 11 (Week 11):

- Update demographics and medical history, including confirmation of lesion size;
- Record prior and concomitant medications, including information on any thyroid-blocking drugs;
- Deliver thyroid-blocking drugs for next visit (only patients eligible for and continuing to Cycle 2);

Note: Patients will not take the thyroid-blocking drugs at this visit but will be instructed to take them 24 hours prior to their next visit (ie, 24 hours prior to study drug administration).

- Perform urine hCG testing in all female patients of childbearing potential (ie, ovulating, premenopausal, and not surgically sterile);
- Collect blood to evaluate serum for ADAs and to measure exploratory biomarkers (from patients who have consented to the procedure);
- Assess AEs;
- Measure weight;
- Perform physical examination;
- Measure vital signs;
- Perform clinical laboratory tests;

Note: Clinical laboratory tests should be performed prior to any imaging.

- Perform triplicate 12-lead ECGs;
- Perform echocardiogram;

Note: LVEF may alternatively be measured using a multigated acquisition scan.

- Perform urinalysis for kidney biomarkers and for microscopic evaluation of sediment; and
- Perform imaging to evaluate disease status (EOT Visit only).

Note: Diagnostic CT scan will be performed in all patients. Brain MRI will only be performed in patients with known brain metastases.

Note: If the patient is continuing to Cycle 2, imaging to evaluate disease status will not be performed.

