6.3.3.2 Visit 12 (Week 0)

Dose 1 of Cycle 2 will be administered at Visit 12. Visit 12 will occur at approximately 2 weeks after Visit 11. The following procedures will be performed at Visit 12 (Week 0):

- Admit to radioactive unit for hospitalization prior to study drug administration;

Note: Patients will be admitted during each IV administration for a total of 48 hours. This hospitalization can be shortened if ^{131}I decay and the patient's clearance allow discharge according to the applicable local regulations on radioactive compound exposure.

Note: Before the patient is released, a leaflet containing information on radioprotection rules and general precautions after radiation treatment will be distributed (see [Appendix F](#)).

- Confirm the ingestion of thyroid-blocking drugs at least 24 hours prior to study drug administration;
- Deliver and confirm the ingestion of thyroid-blocking drugs 1 hour prior to study drug administration;
- Deliver and confirm the ingestion of thyroid-blocking drugs 24 and 48 hours after study drug administration;

Note: If the patient is discharged prior to 48 hours, deliver the thyroid-blocking drugs for 48 hours at 24 hours. Patients will still take the thyroid-blocking drugs 48 hours after study drug administration.

- Perform urine hCG testing in all female patients of childbearing potential (ie, ovulating, premenopausal, and not surgically sterile) prior to study drug administration;
- Assess AEs;
- Perform physical examination prior to study drug administration and at 24 hours after study drug administration;
- Measure vital signs prior to study drug administration and 30 minutes, 5 hours, 24 hours, and 48 hours after study drug administration;
- Administer anti-emetic, anti-histamine, and anti-pyretic premedication therapy approximately 30 minutes prior to the start of the amino acid infusion, according to the site's standard operating procedures;
- Administer saline 0.9% infusion, starting 30 minutes prior to study drug administration and continuing for up to 3 hours after, at a rate of 200 to 300 mL/hour;
- Administer an amino acid solution beginning 30 minutes prior to study drug administration and ending 3 hours after study drug administration at a rate of 250 to 500 mL/hour;

- Administer study drug via slow IV infusion, ie, administer using a shielded infusion device over approximately 3 to 30 minutes, depending on the volume to be injected; and

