- t. Administration of the amino acid solution should be initiated 30 minutes prior to study drug administration, with an infusion rate of 250 to 500 mL/hour. Amino acid solution infusion should be continued for 3 hours after study drug administration. Rates lower than 320 mL/hour are not recommended for commercial solutions. The amino acid solution will be prepared as a compounded product, in compliance with the hospital's sterile medicinal product preparation good practices and according to the composition specified in [Table 5](#).

- u. This will be injected via a slow IV infusion. The study drug will be administered using a shielded infusion device over approximately 3 to 30 minutes, depending on the volume to be injected.
- v. Acceptable time windows for the imaging to evaluate the organ/target lesion uptake are provided in [Table 1](#).
- w. During Dose 1 of the cycle, the planar WB scan will serve as the PD distribution scan.
- x. Imaging to evaluate disease status will be performed with a diagnostic CT scan and brain MRI (if indicated). Diagnostic CT scan will be performed in all patients. Imaging to evaluate disease status after treatment will start 4 weeks after the last CAM-H2 infusion (Dose 2) of the cycle at V19 (Week 8). If a patient cannot receive Dose 2 of a given cycle, his/her imaging to evaluate disease status will start at the theoretical timing for Dose 2 (ie, 4 weeks after Dose 1 of the cycle).
- y. Brain MRI will only be performed in patients with known brain metastases.
- z. Imaging to evaluate disease status will be done at the EOT Visit only. If the patient is continuing to another cycle, imaging to evaluate disease status will not be performed.

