- r. Administration of the amino acid solution should be initiated 30 minutes prior to study drug administration, with an infusion rate of 250 to 500 mL/hour. Amino acid solution infusion should be continued for 3 hours after study drug administration. Rates lower than 320 mL/hour are not recommended for commercial solutions. The amino acid solution will be prepared as a compounded product, in compliance with the hospital's sterile medicinal product preparation good practices and according to the composition specified in [Table 5](#).
- s. This will be injected via a slow IV infusion. The study drug will be administered using a shielded infusion device over approximately 3 to 30 minutes, depending on the volume to be injected.
- t. Acceptable time windows for the imaging to evaluate the organ/target lesion uptake are provided in [Table 2](#).
- u. During Dose 1 of the cycle, the planar WB scan will serve as the PD distribution scan.
- v. Imaging to evaluate disease status will be performed with a diagnostic CT scan and brain MRI (if indicated). Diagnostic CT scan will be performed in all patients. Imaging to evaluate disease status after treatment will start 4 weeks after the last CAM-H2 infusion (Dose 2) of the cycle at V19 (Week 8). If a patient cannot receive Dose 2 of a given cycle, his/her imaging to evaluate disease status will start at the theoretical timing for Dose 2 (ie, 4 weeks after Dose 1 of the cycle).
- w. Brain MRI will only be performed in patients with known brain metastases.

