APPENDIX D: TUMOR MEASUREMENTS AND THE RESPONSE EVALUATION CRITERIA IN SOLID TUMORS VERSION 1.1

Tumor measurements for Response Criteria in Solid Tumors (RECIST) version 1.1 are to be performed for all patients during screening as follows:

- All patients will undergo pre-treatment imaging for eligibility and baseline at Visit 1 with a diagnostic computed tomography (CT) scan for RECIST version 1.1.

Thereafter, tumor measurements and disease response assessments are to be performed as follows:

- Imaging to evaluate disease status after treatment will start 4 weeks after the last CAM-H2 infusion (Dose 2) of the cycle, at Week 8 (Visit 10 or Visit 19), and every 8 weeks thereafter, as long as there is no disease progression. For patients with disease progression, imaging to evaluate disease status will be performed according to the local site standard of care).

During screening, tumor lesions are to be categorized as measurable versus non-measurable and target versus non-target, as follows:

Measurable versus non-measurable

- Measurable: Measurable disease is defined as:
 - Lesions that can accurately be measured in at least 1 dimension (the longest diameter in the plane of measurement to be recorded) with a size ≥ 10 mm by CT scan; and
 - Malignant lymph nodes ≥ 15 mm in short axis when assessed by CT scan. At baseline and in follow-up, only the short axis will be measured and followed.
- Non-measurable: Non-measurable disease is defined as all other lesions, including small lesions (longest diameter < 10 mm or pathological lymph nodes with ≥ 10 to < 15 mm short axis), and truly non-measurable lesions.

Target versus non-target

- Target: Target lesions will include all measurable lesions up to a maximum of 2 lesions per organ and 5 lesions in total, representative of all involved organs. Target lesions are to be selected on the basis of their size (ie, those with the longest diameter) and suitability for accurate repeated measurement. Lymph nodes may be selected as target lesions; they must be defined as measurable, and only the short axis of the node will contribute to the baseline sum. All other pathologic nodes with short axis ≥ 10 mm but < 15 mm should be considered non-target lesions; and
- Non-target: All other lesions not classified as target lesions (or sites of disease) are to be identified as non-target lesions and are to be recorded in the electronic case report form. Measurement is not required.

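### Disease imaging after Week 8 has two calendars for patients continuing to Cycle 2: Tables 1–2 and Appendices D–E imply a Week 16 scan, the visit lists and Tables 7–10 none until about Week 21

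*Combined protocol and SAP*

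**What the plan says.** Weeks below count from Dose 1 of Cycle 1.

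**Imaging tables and appendices.** The Cycle 1 column of Table 2 schedules CT, and brain MRI where brain metastases are known, "Every 8 weeks after Visit 10 (Week 8), as long as the patient had clinical benefit after Cycle 1", provided there is no progression. Table 1 has the same line for Cycle 1 of escalation and, for Cycles 2 to 4, "Every 8 weeks after Week 8, as long as the patient had clinical benefit after the current cycle". Synopsis Tables S2 and S3 repeat both. Appendices D and E place imaging "at Week 8 (Visit 10 or Visit 19), and every 8 weeks thereafter, as long as there is no disease progression", with no condition on clinical benefit or on whether another cycle follows.

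**Visit lists and schedule tables.** At Week 11, Sections 6.2.2.9 and 6.3.2.9 say: "If the patient is continuing to Cycle 2, imaging to evaluate disease status will not be performed". Table 7 footnote cc and Table 9 footnote bb repeat this, and Table 8 footnote z says "If the patient is continuing to another cycle, imaging to evaluate disease status will not be performed". Sections 6.2.3 and 6.3.3 list no diagnostic CT or brain MRI at Visits 12 to 18. Table 10 footnote v starts Cycle 2 disease imaging at Visit 19.

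**Start of Cycle 2.** Section 6.3.3.2 says "Visit 12 will occur at approximately 2 weeks after Visit 11". Section 3.1.2.2 allows any time within two weeks.

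**Column headings.** The Cycle 2 column of Table 2 and the Cycles 2–4 column of Table 1 confine disease imaging to the period after the second dose of the cycle.

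**Follow-up.** Section 3.1.3 says "Imaging to evaluate disease status will begin 8 weeks after the last diagnostic CT scan or brain MRI performed during the study treatment period". Section 6.5 and Table 10 footnote c agree.

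**The concern.** Clinical benefit after Cycle 1 is the condition for the 8-weekly line and also a condition for receiving Cycle 2. Footnote 3 of Table 2 sends patients without benefit to a Week 11 scan, so the 8-weekly line is left to those with benefit, many of whom may continue. A site following Table 2 or the appendices would scan them at Week 16. A site following the visit lists would next scan them at Visit 19.

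The Week 11 notes do not themselves create the conflict, because Week 11 is not on an 8-weekly grid that starts at Week 8. The conflict arises because nothing is listed at Visits 12 to 18.

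PFS, duration of response and PFS in patients with brain metastases (Section 7.2) all use a progression date. Every responder has clinical benefit by definition, so duration of response is measured within the group that the conflict touches.

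**Working it through.** **1. The plan's visit weeks reproduce.** Appendix A puts Visits 10 and 11 on Days 29 and 50 of the Dose 2 count, and Dose 2 is at Week 4.
- Visit 10: 4 + (29 − 1)/7 = Week 8.
- Visit 11: 4 + (50 − 1)/7 = Week 11.

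**2. Imaging tables and appendices, read literally.** 8 + 8 = Week 16.

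**3. Visit lists.** Visit 19 = Week 11 + wait + interval between doses + 4. Delays are from Section 3.1.5.3; visit windows are not added.

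| Timing | Cycle 2 Dose 1 | Dose 2 | Visit 19 | Gap from Week 8 | Visit 19 minus Week 16 |
|---|---|---|---|---|---|
| No wait | 11 | 15 | 19 | 11 weeks | 3 weeks |
| Two-week wait (nominal) | 13 | 17 | 21 | 13 weeks | 5 weeks |
| Both Cycle 2 production delays (2 weeks each) | 15 | 21 | 25 | 17 weeks | 9 weeks |

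The last column is the difference in recorded date for progression in Weeks 8–16 that is found by scan and dated at that scan. At nominal timing, progression in Weeks 16–21 is dated the same on both calendars. PFS runs from enrollment, which adds the same interval to both.

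**4. Mean detection delay.** Assume onset is uniform over the gap and Visit 19 is kept on both calendars.
- 11-week gap: 5.5 weeks on the visit lists, against (8×4 + 3×1.5)/11 = 3.3.
- 13-week gap: 6.5 against (8×4 + 5×2.5)/13 = 3.4, a difference of 3.1.
- 17-week gap: 8.5 against (8×4 + 8×4 + 1×0.5)/17 = 3.8.

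Deaths, and clinical worsening under RANO-BM (Table 14), are not tied to scans. If 10%, 25% or 50% of events are dated without a scan, the 3.1 weeks falls to 2.8, 2.3 or 1.5. At nominal timing, each 10% of patients who continue and progress by scan in Weeks 8–16 adds 0.10 × 5 = 0.5 weeks to mean recorded PFS.

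**5. Median PFS.** Assume exponential progression after Week 8. The figures are the recorded median on the visit lists against the literal calendar.
- All unprogressed patients continue and all events are scan-detected: 21 v 16 weeks for a true median in Weeks 8–16, and no difference for a true median in Weeks 16–21 or above 21.
- 80% continue, true median 15.5, patients who stop scanned at Weeks 11 and 19: 21 v 19.
- 20% continue, true median 12, 20% progressed by Week 8, same scans for those who stop: 19 v 19.
- All continue but 50% of events are dated without a scan, true median 10, 20% progressed by Week 8: 13.9 v 13.9.

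**6. Which patients can continue.** Section 1.3.2 predicts 34.9 mGy/mCi to the kidney. The protocol's own figure reproduces: 400 mCi × 0.0349 = 14.0 Gy for one cycle at Level 4. Against the limit of below 23 Gy:

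| Level (mCi per cycle) | 2 cycles | 3 cycles | 4 cycles |
|---|---|---|---|
| 1 (100) | 7.0 Gy | 10.5 Gy | 14.0 Gy |
| 2 (200) | 14.0 Gy | 20.9 Gy | 27.9 Gy |
| 3 (300) | 20.9 Gy | 31.4 Gy | 41.9 Gy |
| 4 (400) | 27.9 Gy | 41.9 Gy | 55.8 Gy |

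On these predictions Cycle 2 is not reached at Level 4, Cycle 3 is reached only at Levels 1–2, and Cycle 4 only at Level 1. With both maximum delays in Cycles 3–4, the gap would be 3 + 2 + 8 + 12 + 4 = 29 weeks, so that figure concerns Levels 1–2 only.

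**7. Patients with benefit who stop after Cycle 1.** Sections 6.2.2.9 and 6.3.2.9, and footnote 3 of Table 2, tie the Visit 11 end-of-treatment scan to patients without benefit. On that text the last scan is Week 8, and Section 3.1.3 gives 8 + 8 = Week 16. If Visit 11 is treated as an end-of-treatment visit, or as an early-termination visit under Section 6.4, there is a Week 11 scan and follow-up imaging starts at 11 + 8 = Week 19. The text does not settle which applies.

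**The case against.** The strongest reply is that the tables are organised by cycle, so the Cycle 1 line lapses once Cycle 2 starts. The heading of the Cycle 2 column supports this: at nominal timing Week 16 is Week 3 of Cycle 2, before Dose 2 at Week 17. No page prints a calendar of Weeks 8, 16 and 21; it comes from joining the Cycle 1 line to the Cycle 2 column. The reading also fits patients with benefit who stop, if they have no Week 11 scan.

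This part of the reply stands. A reader might infer that Table 2 plainly requires a Week 16 scan and that the visit lists breach it; taken as a whole, the table does not support so firm a claim. Nor may one dismiss the cycle-specific reading on the ground that patients with benefit who stop are certainly scanned at Weeks 11 and 19. Section 6.2.3.10 does make Week 11 the end-of-treatment visit for patients stopped by the kidney limit, but it governs Visits 20, 29 and 38, not Visit 11.

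The reply does not remove the ambiguity. No passage states the cycle-specific reading, Table 2 divides patients by benefit rather than by continuation, and Appendices D and E carry no such limit.

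It is also fair to say that the consequence is limited: these are secondary endpoints in a study with no comparator and no formal sample size calculation. That argues for modest severity, not for leaving the text as it is.

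**Conclusion.** The text is wrong as written: an internal inconsistency of modest severity. For a patient continuing to Cycle 2, one set of pages read literally gives a scan at Week 16, and the other gives none between Week 8 and Visit 19 (nominally Week 21; Weeks 19 to 25 across the allowed timings). Scan-detected progression in Weeks 8–16 is then dated nominally 5 weeks apart (3 to 9).

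This assumes that progression is dated at the detecting scan. The supplied text has no dating or censoring rule; the protocol defers to the SAP and the Imaging Review Charter for detail. A dating rule alone could not supply a scan that was never taken.

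Three larger conclusions might be inferred and are not supported.
- A general 5-week shift in median PFS: 21 v 16 weeks is the extreme in which every unprogressed patient continues and every event is scan-detected. The share who continue is not given.
- Gaps of up to 29 weeks as a feature of the whole trial: on the predicted kidney dose they cannot arise at Levels 3 or 4.
- Damage to the primary response assessment: the Week 8 response scan is the same on both calendars.

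At Level 4 no gap is predicted, but the unsettled Week 11 scan would then apply to every patient with benefit who completes Cycle 1.

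**What to change.** Reconcile Tables 1–2, S2–S3 and 7–10, Sections 6.2–6.3 and Appendices D–E to one disease-imaging calendar. It should say expressly whether the 8-weekly line applies to patients who start another cycle, and whether a patient with benefit who stops after Cycle 1 has a Week 11 scan.

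The option with no added scans is to limit the 8-weekly line, and Appendices D–E, to patients not starting another cycle, counted from the last treatment-period scan as Sections 3.1.3 and 6.5 and Table 10 footnote c already do. Scan spacing then depends on treatment course, so add an interval-censored sensitivity analysis of PFS and duration of response unless the SAP already has one. The cost is a text amendment and one extra analysis.

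The alternative is to enter the 8-weekly scan in the visit lists and schedule tables and amend the Cycle 2 column headings. In expansion this adds one CT, with MRI where brain metastases are known, per continuing patient at Week 16. That week falls on Visit 15 with a two-week wait, on Visit 16 (the Dose 2 admission) with a one-week wait, or on Visit 17 with no wait.
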